8.2.3 Technical Computational Details for Primary Efficacy Analysis

8.2.3.1 Calculation of Binge Eating Days per Week

Binge eating day is defined as a day with at least one confirmed binge eating episode. Binge eating days weekly¹¹ is calculated as the number of confirmed binge eating days divided by the number of non-missing diary days and multiplied by 7 within specified trial day intervals for the mapped week in Table 5.2.-1. In addition, it is required to have non-missing diary data for at least 5 days in calculation of weekly binge eating days. If subjects have missing diary data for more than 2 days at a specific week prior to termination/completion, weekly binge eating days will be set as missing.

Binge eating days per week at Week 1, 2, 3 and 4 (scheduled visits) is equivalent to the calculated weekly binge eating days as specified above. Binge eating days per week for week 6 (scheduled visit) is average of binge eating days on the mapped Week 5 and binge eating days on the mapped Week 6. Similarly, binge eating days per week for week 8(scheduled visit) is average of binge eating days on the mapped Week 7 and/or binge eating days on the mapped Week 8. The derived binge eating days per week at Week 1, 2, 3, 4, 6 and 8 (scheduled visits) will be included in MMRM model for primary efficacy analyses.

8.2.3.2 Pooling Centers

Small centers will be defined as centers that do not have at least one subject with the evaluable primary efficacy endpoint) in each treatment arm. All small centers will be pooled to form "pseudo centers" for the purpose of analysis according to the following algorithm. Small centers will be ordered from the largest to the smallest based on the number of evaluable subjects (ie, subjects who have baseline and at least one post-baseline value for the primary endpoint). The process will start by pooling the largest of the small centers with the smallest of the small centers until a non-small center is formed. This process will be repeated using the centers left out of the previous pass. In case of

ties in center size, the center with the smallest center code will be selected. If any centers are left out at the end of this process, they will be pooled with the smallest pseudo centers, or if no pseudo centers exist, they will be pooled with the smallest non-small center.

8.2.3.3 Data Processing Convention

The SAS code for the PROC MIXED procedure to carry out the above MMRM analysis with an unstructured variance-covariance structure is illustrated as follows:

PROC MIXED:

CLASS treatment center visit subjid;

MODEL change=treatment center visit treatment*visit baseline*visit / S CL DDFM=KENWARDROGER;

REPEATED visit /TYPE=UN SUBJECT=subjid R RCORR;

LSMEANS treatment*visit / PDIFF CL ALPHA=0.05 SLICE=visit;

RUN;

8.3 Key Secondary Efficacy Endpoint

The key secondary endpoint is change from baseline in CGI-S score at Week 8. CGI-S assessment collected at scheduled visits will be mapped to the weeks per specification in Table 5.2-2. This key secondary efficacy endpoint will be analyzed by fitting the MMRM model with treatment group, trial center, visit week, and an interaction term of treatment by visit week as fixed effect terms, and interaction term of baseline value by week as covariates. The similar approach of selection of covariance matrix for MMRM model will be applied as for primary efficacy endpoint.

Sensitivity analyses for the key secondary endpoint will be performed as specification in Section 8.2.2.1 as needed.

8.4 Control of Experiment-wise Type 1 Error

To control the overall experiment-wise type I error at the 0.05 level, a fixed sequence testing approach will be applied. The statistical test will be performed in the following order:

- 1) Change from baseline to Week 7-8 in binge eating days per week between high dose centanafadine and placebo;
- 2) Change from baseline to Week 7-8 in binge eating days per week between low dose centanafadine and placebo;
- 3) Change from baseline to Week 8 in CGI-S score between high dose centanafadine and placebo;

4) Change from baseline to Week 8 in CGI-S score between low dose centanafadine and placebo.

The test for the subsequent hypothesis will be performed only if the test for the previous hypothesis is statistically significant.

8.5 Other Efficacy Endpoints

All other efficacy endpoints will be evaluated at a nominal 0.05 level (2-sided) without adjusting for multiplicity.

Change from baseline in CGI-S score at Weeks 1, 2, 3, 4, and 6 will be analyzed within same methods as specified in Section 8.3.

Cochran-Mantel-Haenszel (CMH) row mean scores differ test controlling trial center will be applied to CGI-C score for LOCF dataset and for OC datasets. Patient Global Impression - Change (PGI-C) score will be analyzed similarly as CGI-C.

Changes from baseline in Y-BOCS-BE total score will be analyzed similarly using MMRM as key secondary efficacy endpoint in Section 8.3. Changes from baseline in PGI-S score and SF 36v2 PCS and MCS scores will be analyzed similarly as changes from baseline in Y-BOCS-BE total score.

Four-week cessation from binge is defined as no binge eating episodes for 28 consecutive days before the last visit. Proportion of subjects with four-week cessation from binge at Week 8/ET will be evaluated by the CMH statistics test controlling for trial center. Risk difference of cessation rate between centanafadine groups and placebo group may be provided as needed.

Change from baseline in number of binge episodes per week will be analyzed similarly using MMRM model as primary efficacy endpoint in Section 8.2.1. Number of binge episodes weekly is number of confirmed binge eating episodes multiplied by 7 and divided by the number of non-missing diary days within trial days interval specified in Table 5.2-1. Number of binge episodes per week at Week1, 2, 3, 4, 6 and 8 (scheduled visits) will be calculated similarly as number of binge eating days as specified in Section 8.2.3.1.

Change from baseline in EDE-Q7 global score at Week 8 and last visit will be analyzed using analysis of covariance (ANCOVA) including treatment and trial center as fixed factors and baseline as covariate.

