5.3 Handling of Missing Data

5.3.1 Missing Data due to Discontinuation

In general, missing data will be handled by analysis of mixed-effect model repeated measures (MMRM) methodology based on observed-case data from scheduled visits under the assumption of missing at random. MMRM assume data are missing at random (MAR), which is a reasonable assumption in longitudinal clinical trials¹ in the binge eating disorder population. However, the possibility of "missing not at random" (MNAR) data can never be ruled out.

The observed-cases (OC) dataset will consist of actual observations recorded at each visit during the double-blind treatment period and no missing data will be imputed. MMRM,

a Relative to the first day of double-blind IMP in the double-blind treatment period.

b Evaluations occurring more than three days after the last double-blind dosing date and evaluations occurring during the follow-up period will be excluded from analyses.

model-based imputation model, and pattern-mixture model will be performed on the OC dataset.

The last-observation-carried-forward (LOCF) data set will include data recorded at a scheduled visit or, if no observation is recorded at that visit, data carried forward from the previous visit. Baseline data will not be carried forward to impute missing values for the LOCF data set. For categorical efficacy variables, OC analyses will be performed in addition to LOCF analyses.

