8.1 Estimands

8.1.1 Primary Estimand

The primary clinical question of interest is: what is the treatment difference in binge eating days per week after 8 weeks of centanafadine treatment compared to placebo treatment in adult subjects with moderate to severe BED, where no subject would discontinue treatment due to any reason?

The primary estimand has the following attributes:

- Population: adult subjects with moderate to severe BED who meet the inclusion/exclusion criteria.
- Endpoint: change from baseline in binge eating days per week at Weeks 7-8.
- Intercurrent events: premature treatment discontinuation.
- Treatment condition: one of the randomized treatment groups of the following per protocol: high dose centanafadine 400 mg TDD, low dose centanafadine 200 mg TDD, or placebo.
- Population-level summary: difference in mean of endpoint between treatment conditions.
- Rationale for estimand: the hypothetical estimand is to evaluate the pharmacological effect if no withdrawals had occurred. It is justifiable since the focus is on the pharmacological effect of the drug additional to non-specific effects. Subjects who withdraw from a symptomatic IMP treatment either could have lost the treatment effect if the subjects had not taken any other symptomatic medication after withdrawal or could have the treatment effect masked if the subjects had taken other symptomatic medication after withdrawal. In those cases, any observations taken after subjects stop IMP will most likely not contribute to relevant information about the pharmacological effect of the drug. Therefore, the last collected efficacy assessment after premature trial discontinuation will be performed only once at the ET Visit.

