8.1.2 Secondary and Other Estimands

The clinical question of interest for the key secondary estimand is: what is the treatment difference in CGI-S Score after 8 weeks of centanafadine treatment compared to placebo treatment in adult subjects with moderate to severe BED, where no subject would discontinue treatment due to any reason?

The key secondary estimand has similar attributes to the primary estimand except that key secondary endpoint is change from baseline in CGI-S score at Week 8. Other estimands have similar attributes to the primary and key secondary estimands.

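### CGI-C and PGI-C are tested only on LOCF and observed-case data, although the SAP's estimand for them supposes that nobody discontinues; a MAR-based main analysis would fit it (minor)

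*SAP*

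**What the plan says.** **Estimand.** SAP 8.1.1 explains that "the hypothetical estimand is to evaluate the pharmacological effect if no withdrawals had occurred". SAP 8.1.2 asks the key secondary question in a setting "where no subject would discontinue treatment due to any reason" and adds: "Other estimands have similar attributes to the primary and key secondary estimands". SAP 6.3 lists CGI-C and PGI-C among the other efficacy endpoints, so that sentence covers them.

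**Missing data.** SAP 5.3.1 opens with "In general, missing data will be handled by analysis of mixed-effect model repeated measures (MMRM) methodology based on observed-case data from scheduled visits", under MAR. It then defines an LOCF data set in which, "if no observation is recorded at that visit, data carried forward from the previous visit", and sets a separate rule: "For categorical efficacy variables, OC analyses will be performed in addition to LOCF analyses".

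**Analysis.** SAP 8.5 states that a centre-stratified CMH "row mean scores differ test controlling trial center will be applied to CGI-C score for LOCF dataset and for OC datasets", and that "Patient Global Impression - Change (PGI-C) score will be analyzed similarly as CGI-C". SAP 8.6 leaves both endpoints out of the by-week ANCOVA. Appendix 4 lists one LOCF and one OC table for each (CT-5.4.1 and CT-5.4.2; CT-5.9.1 and CT-5.9.2).

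**Protocol.** Protocol 9.4.1.4 prescribes CMH with trial center as the controlling factor but names no LOCF data set. SAP Section 15 does not record the choice of LOCF.

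**The concern.** The estimand asks what the contrast would have been had everyone stayed on treatment. LOCF freezes a dropout at the last rating obtained, so it answers a question about the last on-treatment rating. OC at Week 8 describes those still observed. Neither uses the earlier ratings of those who leave to predict their Week 8 rating, as a MAR method would.

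The plan also treats matched scales differently. CGI-S, PGI-S, CGI-C and PGI-C are all 7-point ratings scheduled at Weeks 1, 2, 3, 4, 6 and 8 (Protocol Table 1.3-1). CGI-S and PGI-S get MMRM under MAR (SAP 8.3 and 8.5). CGI-C and PGI-C get no MAR-based analysis. The change ratings could therefore disagree with the severity ratings because of the missing-data rule and not because of the drug.

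Unequal dropout is plausible on the protocol's own text, since Protocol 4.2 and 4.3 describe dose-dependent adverse events. What is at stake is the reading of two supportive endpoints in a proof-of-concept trial.

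**Working it through.** **The plan's own figures.** SAP Section 4 assumes a difference of 1.1 and SD 1.7 on the primary endpoint. With 38 per arm, 1.1 / (1.7 × √(2/38)) = 2.82, and power = Φ(2.82 − 1.96) = 80.5% (79.5% by noncentral t). This reproduces the plan but does not bear on CGI-C, for which no power is stated. The step from 114 to 126 implies 12/126 = 9.5% non-evaluable. I use that only as an anchor; the documents give no dropout rate by arm and no CGI-C means.

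**Step 1: LOCF by formula (assumed inputs).** Week 8 improvement from no change is 1.5 points on placebo and 2.0 on active, so the true difference is 0.50. Dropouts have their last rating at Weeks 1, 2, 3, 4 or 6, equally often. With dropout d and w the mean fraction of the final improvement reached by then:

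LOCF mean = final improvement × [(1 − d) + d × w]

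- Linear growth to Week 8: w = (1+2+3+4+6)/(5×8) = 0.40.
- Plateau from Week 4: w = (0.25+0.5+0.75+1+1)/5 = 0.70.

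| Dropout, placebo / active | Linear | Plateau |
|---|---|---|
| 9.5% / 9.5% | 0.50 × 0.943 = 0.47 | 0.50 × 0.9715 = 0.49 |
| 5% / 15% | 2.0×0.91 − 1.5×0.97 = 0.365 | 2.0×0.955 − 1.5×0.985 = 0.432 |
| 5% / 20% | 2.0×0.88 − 1.5×0.97 = 0.305 | 2.0×0.94 − 1.5×0.985 = 0.403 |
| 15% / 5% | 2.0×0.97 − 1.5×0.91 = 0.575 | 2.0×0.985 − 1.5×0.955 = 0.538 |

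Equal dropout costs 3-6%. Unequal dropout moves the contrast towards zero when active loses more, and away from zero when placebo loses more.

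**Step 2: LOCF and OC by simulation (different assumed inputs).** 42 per arm, 7 center strata, integer ratings 1-7, placebo means 3.6, 3.3, 3.1, 2.9, 2.7 and 2.5 at Weeks 1, 2, 3, 4, 6 and 8, SD 1.1, 2000 runs per scenario. Differences are active minus placebo; negative favours active.

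| Scenario (dropout, placebo / active) | Full data | LOCF | OC |
|---|---|---|---|
| No effect, random, 9.5% / 20% | 0.00 | +0.07 | 0.00 |
| No effect, random, 9.5% / 30% | +0.01 | +0.14 | +0.01 |
| No effect, poor responders leave, 10% / 29% | −0.01 | +0.22 | −0.10 |
| Effect, random, 9.5% / 30% | −0.44 | −0.26 | −0.44 |
| Effect, placebo poor responders 20%, active random 10% | −0.45 | −0.62 | −0.36 |

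In the third row LOCF rejects in 11.9% of runs and OC in 6.8%. In the fourth, rejection is 49% with full data, 20% with LOCF and 40% with OC; the OC loss there is lost sample size, not bias.

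**Step 3: is the gap filled elsewhere?** Table numbers in Appendix 4 run from CT-5.4.2 to CT-5.5.1.1 and from CT-5.9.2 to CT-5.10.1.1 with no blacked-out entry between them. No multiple-imputation or MMRM analysis of CGI-C or PGI-C is stated.

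**The case against.** The SAP does not call the other estimands identical, only similar, and the MMRM statement is qualified as general. The LOCF-plus-OC rule for categorical variables is prespecified in the same section, and CMH is the protocol's own test. OC is reported beside LOCF, and CGI-S and PGI-S already give MAR-based global ratings. All this stands and limits the weight of the point. It does not remove the mismatch: no other estimand is stated for these endpoints, and neither data set targets the one implied. The ordinal scale does not explain the difference either, since the SAP models CGI-S and PGI-S as continuous.

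The visit rules also soften the picture. Both scales are scheduled at Week 8/ET, and SAP Table 5.2-2 maps Days 50-63 to Week 8 unless the rating falls over three days after the last dose. A late early-terminator can therefore enter the Week 8 OC analysis, which is close to, but not exactly, completers. Step 1 has no such dropouts and puts three-fifths of them at Weeks 1-3, which raises the distortion.

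Two stronger readings are tempting. A reader might infer that unequal dropout also biases the OC test. It does not by itself: with random dropout at 9.5% v 30% OC stays on the full-data value. A reader might also infer that LOCF always penalises the active arm. The fourth row of the first table and the last row of the second show the opposite. Lack of baseline adjustment adds little, since both scales are already rated relative to baseline.

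**Conclusion.** The point holds as a minor inconsistency between estimand and analysis. LOCF attenuates slightly with equal dropout (3-6% at an assumed 9.5%) and distorts in either direction when dropout differs: an assumed true 0.50 becomes 0.37-0.43 at 5% v 15% with active higher, and a true 0.45 becomes 0.62 when placebo non-responders leave. OC shifts by about 0.05-0.10 in the simulated cases where dropout depends on response and the arms differ in how many leave or why. That is the case that MAR methods address.

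These sizes rest on assumed trajectories and dropout, so they show a possible range and are not a forecast. Week 8 as the time point is inferred from its being the last treatment visit; the SAP sets none for these endpoints. A reader might infer a threat to the trial's main conclusions. The documents do not support that: both endpoints are tested at a nominal level and lie outside the four-step sequence of SAP 8.4.

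**What to change.** In SAP 8.5, name Week 8 as the main time point for CGI-C and PGI-C and make the main analysis MAR-based, by either route:

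- multiple imputation under MAR, then the protocol's centre-stratified CMH row-mean-score test, with the pooling rule stated. SAP 8.2.2.3 already names the SAS MI and MIANALYZE procedures; or
- the MMRM of SAP 8.3, with baseline CGI-S (for CGI-C) or baseline PGI-S (for PGI-C) by visit as covariate, since a change rating has no baseline value of its own.

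Keep the OC and LOCF CMH tests as supportive, with their planned tables, and record the change in Section 15. The other consistent course is to state in 8.1.2 a different estimand for these two endpoints.

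The cost is SAP wording and a little programming. If MMRM is used, a 7-point rating is treated as continuous, as the SAP already does for CGI-S and PGI-S.

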8.6 Exploratory Analysis

Exploratory efficacy analyses will be presented in Statistical Documentation as needed.

Line plots for mean of primary efficacy endpoint will be presented by week to explore missing patterns across the treatment groups.

Treatment-by-center interaction will be assessed at Week 8 by including the treatment-by-center-by-visit interaction in the models.

The primary, key secondary and other efficacy endpoints will be analyzed using ANCOVA model, including treatment and trial center as fixed factors and baseline as covariate, will be also performed by week, except the endpoints of frequency of subjects with four-week cessation from binge at Week 8/ET, CGI-C and PGI-C.

Y-BOCS-BE subscale scores for obsession and compulsion maybe explored using similar MMRM model and ANCOVA for Y-BOCS-BE total score. In addition, percentage of subjects in different severity (i.e., sub-clinical, mild, moderate, severe, and extreme) will be provided by week and treatment group.

EDE-Q7 subscale scores for dietary restraint, shape/weight overvaluation, and body dissatisfaction will be analyzed using same model for EDE-Q7 total score.

Cohen's D effect size will be provided for the efficacy endpoints as continuous variables, if necessary. Cohen's D effect size is the difference between the two means divided by their standard deviation¹². Least square mean (LSMean) difference of treatment effects between centanafadine and placebo groups, and the standard error of the difference will be obtained from MMRM, or ANCOVA. Let n₁ and n₂ denote the respective sample sizes of the two groups for pair-wise comparison,

Cohen's D Effect Size = (LSMean centanafadine – LSMean placebo) /
$$\sigma$$
, where $\sigma = \frac{\text{Stderr}}{\sqrt{\frac{1}{n_1} + \frac{1}{n_2}}}$.

Subgroup analyses for primary efficacy endpoints may be explored by age (<40 years old vs >=40 years old), gender (Male vs Female), race(Caucasian vs non-Caucasian) or other baseline characteristics.

9 Safety Analyses

In general, analysis of safety data will be performed for safety analysis set on observed case (including last visit) unless otherwise specified.

9.1 Extent of Exposure

The number and percentage of subjects who receive IMP, will be presented by week and by treatment group. Each dosing week will be based on the actual week, e.g., Day 1 to 7 in Week 1, Day 8 to 14 in week 2, etc. This summary will be performed on randomized analysis set.

The mean daily dosage will be summarized by week and treatment group using descriptive statistics for safety analysis set. The mean daily dosage per subject per week will be determined for each week of the study. This will be calculated by dividing the sum of individual total doses by the number of days in the week interval. The summary will contain for each treatment group the number of subjects receiving IMP, and the mean and range of the mean daily dose for each week.

9.2 Adverse Events

All AEs will be coded by system organ class (SOC) and Medical Dictionary for Regulatory Activities (MedDRA) Preferred Term (PT). The incidence of the following events will be summarized by treatment group:

- a) Treatment-emergent AEs (TEAEs)
- b) TEAEs by severity
- c) TEAEs potentially causally related to the IMP
- d) TEAEs with an outcome of death
- e) Serious TEAEs
- f) TEAEs leading to discontinuation of the IMP
- g) Treatment-emergent Adverse Events of Special Interest (AESI) related to Rash
- h) TEAEs related to Abuse
- i) TEAEs involving Medication Handling Irregularities (MHI)

AEs will be classified by primary SOC and PT according to MedDRA. AEs that are gender-specific, e.g., ovarian cancer, will have their incidence rates evaluated for the specific gender. TEAEs are all adverse events which started after start of IMP; or if the event was continuous from end of the single-blind placebo run-in period and was worsening, serious, study drug related, or resulted in death, discontinuation, interruption, or reduction of study therapy. Adverse events occurring up to 30 days after the last day of double-blind dosing will be included in the summary tables.

Incidence of TEAEs will be summarized by treatment group. Incidence of TEAE of at least 5% in either centanafadine group and greater than placebo will be provided by treatment group, SOC and MedDRA PT.

AESI related to rash will be selected from AESI worksheet and AE CRF. TEAEs related to abuse will be searched based on specified MedDRA PTs. TEAEs involving MHI will be selected from Events Subject to Additional Monitoring (ESAM) form and AE CRF.

